#### **6.1.3.2 Handling of missing values/censoring/discontinuations**

Assuming missing at random, a subject with missing value at a time point will still contribute to the estimation of the treatment effect at that particular time point as the likelihood-based repeated measures analysis borrows information from non-missing values of this subject and other subjects.

#### **6.1.3.3 Graphical presentation of results**

If there are sufficient data to analyze, then the time to headache response, time to pain free response and time to recurrence curves, using Kaplan-Meier estimates will be constructed by dose. A clustered log-rank test for correlated survival data will be performed to compare the time to event curves between treatments while hazard ratios will be estimated by the Cox proportional hazard frailty model with CH type and baseline headache severity or frequency included as covariates as appropriate. If subjects do not have an event, they will be censored at their last available visit. These analyses will only be conducted if the primary analysis indicates a significant result and if there is sufficient data.

#### **6.1.4 Supportive analyses**

The McNemar test with or without stratification by CH type may also be used to compare headache response rates between treatments at 30 minutes post-dosing only.

If there are sufficient data to analyze, a Cox proportional hazard model with dose and CH type as classification factors and headache severity as a time dependent covariate will be used to analyze time to 100% oxygen therapy or sumatriptan. A random subject effect will be included in the model as well to account for the correlation among measurements from the same subject. This model will only be performed if the primary analysis indicates a significant result and there is sufficient data.

Joint modelling of the headache response and time to 100% oxygen therapy or sumatriptan data may be attempted as appropriate. This analysis will only be performed if a good response rate at 30 minutes versus placebo is detected.

Finally to avoid reducing statistical efficiency due to analyzing the dichotomized data, the headache severity measurements over time may be analyzed using a proportional-odds model similar to the aforementioned logistic regression model.

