#### **11.4.4 Supportive analyses**

Additionally 100% oxygen therapy will be included in the logistic regression model described above as a time dependent covariate so headache response measurements after 100% oxygen therapy can be included in the analysis.

The McNemar test with or without stratification by CH type may also be used to compare headache response rates between treatments at each time point.

A Cox proportional hazard model with dose and CH type as classification factors and headache severity as a time dependent covariate will be used to analyze time to 100% oxygen therapy. A random subject effect will be included in the model as well to account for the correlation among measurements from the same subject. Percentage of subjects receiving 100% oxygen therapy at each time point will be tabulated by treatment.

Joint modelling of the headache response and time to 100% oxygen therapy data may be attempted as appropriate.

Finally to avoid reducing statistical efficiency due to analyzing the dichotomized data the headache severity measurements over time may be analyzed using a proportional-odds model similar to the aforementioned logistic regression model.

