Subjects will be required to complete a patient diary to document the pain severity and pain relief before and after the administration of the study medication. In case the pain is not responding to the administered study drug after 30 minutes, subjects will be allowed to use only 100% oxygen or sumatriptan as a rescue management. If applicable and feasible, subjects in Period 1 may return to the study center for follow-up within 24 hour post treatment administration. The subjects will have a follow-up within 24 hours of the study drug administration in Period 2 where a PK sample will be collected, with a second PK sample collected to 1 to 2 hours after the 1st PK sample. In case the follow-up visit in Period 2 falls on a weekend, a window of up to 48 hours may be considered.

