#### **6.1.1 Variables**

Percent (%) of subjects with headache response defined as very severe, severe, or moderate pain before dosing that becomes mild or nil at 30 minutes post-dosing is the primary variable.

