#### **6.1.2 Descriptive analyses**

If the second cohort (0.9 mg dose) is assessed then cohort will serve as a grouping factor for all relevant data listings.

The headache response will be defined at each post-dose timepoint separately and will be summarized by cohort, treatment and visit/timepoint using frequency tables. Percentage of subjects having received 100% oxygen therapy or sumatriptan at each time point will be tabulated by cohort and treatment.

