#### **6.1.3.1 Sensitivity analyses**

Subjects are able to take a rescue medication at least 30 minutes following study medication administration. As a sensitivity analysis, the logistic regression analysis shall be repeated on all timepoints, where only the timepoints with at least 50% of non-missing data will be kept.

The logistic regression analysis with baseline headache severity (very severe, severe or moderate), CH type (episodic or chronic), dose (0 for placebo, 1.5 mg or 0.9 mg for SOM230), time and dose by time interaction as fixed effects and subject as a random effect will be used to assess the effect of SOM230 on headache response. Dose and time will be included as categorical variables in the model. Placebo adjusted headache response rate at each time point will be provided. Headache response measurements after 100% oxygen therapy or sumatriptan will be set to missing, which will be considered as missing at random. The frequency and percentage of subjects with each response shall be displayed, along with the mean estimates, 90% confidence interval and p-value from the logistic regression analysis.

The sensitivity logistic regression will only be performed if the primary analysis indicates a significant result.

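### The time-to-rescue Cox model adjusts for post-dose pain, so its dose hazard ratio is not the overall SOM230-versus-placebo effect on rescue

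*SAP*

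**What the plan says.** SAP 6.1.4 plans a Cox model with dose, CH type, a random subject effect and "headache severity as a time dependent covariate will be used to analyze time to 100% oxygen therapy or sumatriptan". Protocol 11.4.4 has the same model with oxygen as the only event: "headache severity as a time dependent covariate will be used to analyze time to 100% oxygen therapy". The SAP adds a precondition: "This model will only be performed if the primary analysis indicates a significant result and there is sufficient data".

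On when rescue can occur, SAP 6.1.3.1 says "Subjects are able to take a rescue medication at least 30 minutes following study medication administration", and SAP 1.4 ties it to lack of response: "In case the pain is not responding to the administered study drug after 30 minutes". The primary variable in SAP 6.1.1 is built from the same pain scale: "very severe, severe, or moderate pain before dosing that becomes mild or nil at 30 minutes post-dosing".

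For time to response, time to pain free and time to recurrence, SAP 6.1.3.3 plans Kaplan-Meier curves, a clustered log-rank test and a "Cox proportional hazard frailty model with CH type and baseline headache severity or frequency included as covariates as appropriate". Time to rescue is not on that list. Otherwise rescue appears only as frequencies, in SAP 6.1.2 ("Percentage of subjects having received 100% oxygen therapy or sumatriptan at each time point will be tabulated by cohort and treatment") and in SAP 6.2.1.2. Neither document says which effect the dose HR in the rescue model is meant to estimate.

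**The concern.** A patient is at risk of rescue only from 30 minutes after dosing. Any severity value used over that time is therefore a post-dose value. SOM230 is meant to lower it, and it is the stated reason for taking rescue. Adjusting for it removes the part of the drug's effect that acts through pain relief, and the dose term keeps only what is left.

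The model runs only after a significant primary result, that is, when SOM230 appears to have changed pain and this covariate carries most of the effect. An HR near 1 could then be reported as no effect on rescue, although fewer patients needed rescue or they needed it later.

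**Working it through.** **1. Which severity is meant.** Where the SAP wants the pre-dose value it says baseline severity (6.1.3, 6.1.3.1, 6.1.3.3). Protocol 11.4.4 also uses the term time-dependent covariate for oxygen, so that measurements after oxygen can be kept, which means a value that changes within an attack. Severity in the rescue model is therefore current pain.

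**2. What the dose term estimates.** Write the rescue hazard as h(t) = h0(t) × exp(γS(t) + β·dose), with S(t) = 1 for non-response and 0 for response. The planned model targets β. If the drug acts only through pain, β = 0 and the HR is 1. The overall hazard in an arm is h0(t) × exp(β·dose) × [π(t)·exp(γ) + 1 − π(t)], where π(t) is the share of at-risk patients not responding. That share differs between arms.

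**3. Size at 30 minutes, by hand.** Protocol 11.6 assumes response rates of 30% and 72%, so π is 0.70 on placebo and 0.28 on SOM230. The severity HR, exp(γ), is not in the documents; 10, 4 and 2 are assumed. With β = 0 the overall hazard ratio at 30 minutes is:

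- severity HR 10: (0.28×10 + 0.72)/(0.70×10 + 0.30) = 3.52/7.30 = 0.48
- severity HR 4: (0.28×4 + 0.72)/(0.70×4 + 0.30) = 1.84/3.10 = 0.59
- severity HR 2: (0.28×2 + 0.72)/(0.70×2 + 0.30) = 1.28/1.70 = 0.75

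**4. Large-sample check.** This used 200,000 subjects, both periods, and a grouped-data proportional hazards fit without frailty. Assumed: five intervals, interval rescue rate 0.3 or 0.6 in non-responders, and spontaneous resolution of 0 or 10% per interval.

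| Severity HR | Direct drug HR | Dose HR, severity left out | Dose HR, current severity in |
|---|---|---|---|
| 10 | 1 | 0.44-0.47 | 0.99-1.01 |
| 4 | 1 | 0.59-0.62 | 0.99-1.01 |
| 2 | 1 | 0.75-0.78 | 0.99-1.01 |
| 10 | 0.80 | 0.37-0.40 | 0.80 |
| 4 | 0.80 | 0.49-0.51 | 0.80 |
| 2 | 0.80 | 0.61-0.63 | 0.80 |

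The dose HR of about 1 coexists with real differences in cumulative rescue, for example 58.7% on placebo against 31.7% on SOM230 (HR 0.44 without severity).

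**5. The model as planned, with subject frailty.** Response rates of 30% and 72% and the correlation of 0.25 come from protocol 11.6. The other inputs are assumed:

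- pre-dose moderate/severe/very severe pain 30/40/30%, and 30% chronic CH;
- responders nil or mild (half each) from 30 minutes, and non-responders at their pre-dose level until they resolve;
- frailty SD 0.7, and severity updated every 15 minutes;
- follow-up to 120 minutes with 15% resolution per 15 minutes, or to 60 minutes with 30%;
- rescue hazards per minute for pain 0 to 4: strong link .0005/.002/.02/.04/.06, moderate link .004/.006/.010/.016/.024, very weak link .0100/.0110/.0121/.0133/.0146.

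The HRs are averages of the log HR over 80 runs of 200 subjects, with Monte Carlo standard error at most 0.025. Ranges span the two follow-up settings.

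| Link to pain, direct HR | Pre-dose severity | Time-dependent, linear | Time-dependent, categorical |
|---|---|---|---|
| Strong, none | 0.37-0.38 | 0.84-0.86 | 1.02-1.03 |
| Strong, none, 20% diary error | – | 0.78-0.79 | 0.87-0.89 |
| Moderate, none | 0.66-0.69 | 1.01 | 1.01-1.02 |
| Very weak, 0.6 | 0.56-0.58 | 0.61-0.63 | 0.61-0.63 |
| Strong, 1.3 | 0.44 | 1.07-1.08 | 1.30-1.31 |

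Refitting without the frailty term gave similar values: 0.40 against 0.88-0.89 and 1.03 for the strong link.

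**6. At 23 patients.** Over 1,000 simulated trials, with significance taken as two-sided p<0.10 in favour of SOM230, the primary analysis was significant in 92.5%. Among those trials, a benefit on rescue was found at two-sided p<0.10 as follows.

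| Link to pain | Pre-dose severity | Time-dependent, linear | Time-dependent, categorical |
|---|---|---|---|
| Strong | 58-71% | 7-11% | 4-7% |
| Moderate | 18-20% | 4-5% | 4-5% |
| Very weak, direct HR 0.6 | 26-39% | 20-30% | 20-29% |

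About 12-26 rescue events per 23 patients are expected under these assumptions. No period effect was simulated.

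**The case against.** The strongest reply is that the conditional effect may be what the sponsor wanted. SAP 6.1.4 says only that time to rescue will be analysed. It promises no treatment comparison, whereas 6.1.3.3 does promise one and there uses baseline severity. Responses after rescue are set to missing and treated as missing at random, so a model of what drives rescue given current pain has a natural use. It also stands directly before the optional joint modelling. This reading is plausible, but the documents do not state it, and an unlabelled dose HR remains open to misreading.

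The overall contrast is partly available already, since rescue percentages are tabulated whatever the primary result. That limits the harm. The tables do not, however, give a time-to-event estimate with an interval.

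Redacted text in the exploratory sections may hold another rescue analysis. So one can say only that no other firm inferential analysis of time to rescue is visible. What this model estimates is unaffected.

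The simulated sizes rest on assumed hazards, and the detection rates score a conditional model as a test of an overall effect. Both points are fair: the figures illustrate and do not predict. The SAP does not define a significant primary result either. Reading protocol 11.6 as one-sided 0.10 lets the model run in 96% of simulated trials, and adding its 30% difference criterion gives 88%, against 92.5% above. With so few events either model is imprecise, and the requirement for sufficient data may stop both.

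**Conclusion.** The concern holds. The dose HR from the planned rescue model is conditional on current pain and does not measure the overall SOM230-versus-placebo difference in time to rescue. This follows from the structure of the model and needs no simulation, provided pain drives rescue and SOM230 lowers pain.

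The size in this trial cannot be known, because the documents give no rescue hazards. Under the assumptions shown, the gap runs from large (0.37-0.38 against 0.84-1.03) to nearly nothing when rescue hardly depends on pain (0.56-0.58 against 0.61-0.63). If the drug itself raised rescue at equal pain, the planned HR would point the other way from the overall one (1.07-1.31 against 0.44).

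The consequence is minor and the change optional. The study is non-confirmatory, the model is supportive with two preconditions, and time to rescue is not a visible primary or secondary endpoint.

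**What to change.** In SAP 6.1.4, under the same preconditions and for the same event, add a Cox model with dose and CH type as factors, the pre-dose severity of the treated attack as a covariate, and a random subject effect. Use it for the dose comparison on rescue. This matches the baseline adjustment in SAP 6.1.3.3.

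Keep the time-dependent-severity model as exploratory. State whether severity enters as linear or categorical, label the result as conditional on current pain, and state that its dose HR is not read as the drug's effect on rescue. Add that both HRs remain confounded with period, as protocol 3.2 acknowledges for the treatment effect in general.

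The cost is one extra supportive model and a documented departure from protocol 11.4.4. No new data are needed: pre-dose severity is already used in SAP Table 4-1, and the diary in protocol 8.3.2 records rescue use and its time. A written amendment under protocol 13.1 is needed only if the protocol wording is changed as well.

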## **6.2 Secondary and exploratory objectives**

### **6.2.1 Efficacy/Pharmacodynamics**

#### **6.2.1.1 Variables**

The percentage of subjects who are pain free at 30 minutes pose dose is one of the secondary endpoints.

Corporate Confidential Information

#### **6.2.1.2 Descriptive analyses**

Number and percentage of subjects pain free and of subjects reporting improvement of associated autonomic symptoms (for example, lacrimation, blushing, pupil constriction, etc.) over time will be tabulated by dose.

Number and percentage of subjects receiving rescue medication at or after 30 minutes.

#### **6.2.1.3 Statistical model, assumptions and hypotheses**

Pain free data will be analyzed using the same approach described for the primary variable. Pain free response measurements after 100% oxygen therapy or sumatriptan will be set to missing, which will be considered as missing at random.

## **6.2.2 Pharmacokinetic/pharmacodynamic interactions**

The relationship between reconstructed individual PK profiles with various efficacy/PD variables will be explored as appropriate and the results reported in a separate report.

## **7 Statistical methods for safety and tolerability data**

### **7.1.1 Variables**

Adverse events, vital signs (blood pressure, pulse rate, body temperature), ECG intervals, laboratory measurements, as well as subject demographics, baseline characteristics, and treatment information.

### **7.1.2 Descriptive analyses**

#### **Subject demographics and other baseline characteristics**

All data for background and demographic variables will be listed by cohort, treatment and subject. Summary statistics will be provided by cohort and treatment.

Relevant medical history, current medical conditions, results of laboratory screens, drug tests and any other relevant information will be listed by cohort and subject.

#### **Treatment**

Data for study drug administration, rescue medications and concomitant therapies will be listed by cohort, treatment and subject as appropriate.

#### **Vital signs**

All vital signs data will be listed by cohort, treatment, subject, and visit/time and if ranges are available abnormalities (and relevant orthostatic changes) will be flagged. Summary statistics will be provided by cohort, treatment and visit/time.

#### **ECG evaluations**

All ECG data will be listed by cohort, treatment, subject and visit/time, abnormalities will be flagged. Summary statistics will be provided by cohort, treatment and visit/time.

#### **Clinical laboratory evaluations**

All laboratory data will be listed by cohort, treatment, subject, and visit/time and if normal ranges are available abnormalities will be flagged. A separate listing is provided presenting all parameters in a subject with any abnormal values. Summary statistics will be provided by cohort, treatment and visit/time.

#### **Adverse events**

All information obtained on adverse events will be displayed by treatment and subject.

The number and percentage of subjects with adverse events will be tabulated by body system and preferred term with a breakdown by cohort and treatment. An adverse event starting in one period and continuing into the next period is counted only in the onset period. A subject with multiple adverse events within a body system is only counted once towards the total of this body system and treatment.

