### 3.1    **Study design**

This non-confirmatory study will be conducted in 2 cohorts using a one-sequence two-period design to compare SOM230 vs. Placebo. Following observed efficacy and safety signals in Cohort 1 with the 1.5 mg dose, cohort 2 of the study assessing efficacy of a lower SOM230 dose (0.9 mg) may be considered.

Two consecutive attacks will be treated: first attack will be treated with placebo (Period 1) and the following attack will be treated with SOM230 (Period 2). Approximately 30 patients will be enrolled in Cohort 1 to receive Placebo s.c. single dose in Period 1 then SOM230 1.5 mg s.c., a single dose in Period 2. Each study cohort will consist of a 21 day screening period, a baseline period of 3 days prior to the Baseline Visit, a treatment period (Period 1) lasting up to 3 days then a treatment period 2 of up to 3 days, followed by an end of study visit 3 days after study drug administration in Period 2. The subjects will have up to 5visits. Similarly, in Cohort 2 approximately 30 subjects will receive placebo s.c. single dose in Period 1 and SOM230 0.9 mg s.c., as a single dose in Period 2. Each subject will be instructed to self-administer (or assisted by a helper, or by medical staff if domiciled at a clinic) the study medications at the beginning of the CH attack (as early as possible; within 10 minutes of start of attack when pain is at least moderate). In case patient experiences CH attacks PRIOR to administering study treatment in Period 1 they can use 100% O2 or their conventional treatment to manage their acute attacks experienced before Period 1. If the subject does not have a headache attack in **72 hours post-baseline** or 72 hours post Period 1 treatment the subject will be excluded from the study. Subjects will be required to complete a patient diary to document the pain severity and pain relief before and after the administration of the study medication (**Figure 3-1**). In case the pain is not responding to the administered study drug after 30 minutes, subjects will be allowed to use only 100% oxygen as a rescue

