### 4.1 Inclusion criteria

1. Subject is male or female age 18-65 inclusive.
2. Written informed consent must be obtained before any assessment is performed.
3. Subjects must have established diagnosis of episodic cluster headaches (CH) or chronic CH, averaging 2-6 headache attacks per day each lasting at least 45 minutes without treatment, not to exceed 6 attacks per day within the last year.
4. Able to communicate well with the investigator, to understand and comply with the requirements of the study, as well as accepting NOT to share any study information through social media during their participation in the study.
5. Subject is able to self-inject medication subcutaneously or have the assistance of a helper on an out-patient basis, if subject is not domiciled in a clinic for the study.

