## **6.9      Rescue medication**

Subjects will be allowed to use 100% oxygen as rescue medication during the study as described in [Section 7.1](#). If subjects require use of other rescue medication, they must contact the site immediately to be discontinued from the study. Every effort must be made to obtain study data for at least 24 hours after study medication has been administered. Use of rescue medication must be recorded on the Concomitant medications/Significant non-drug therapies CRF after start of study drug.

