## 8 Procedures and assessments

**Table 8-1 Assessment Schedule, (Cohorts 1 &2)**

 Visit structure given for internal programming purpose only.

 In the event the subject requires SOC treatment for CH or a recurrent CH attack, the subject must contact the site, every effort must be made to discontinue the subject after 24 hours of taking the study medication, all EOS evaluations should be performed if a subject is discontinued.

 If subject is not domiciled in a clinic for the study, study drug will be administered at home, before study visits.

 If possible in Period 1, the subject may have a follow-up visit as soon as possible within 24 hours of the dose. The collected PK sample must be obtained as soon as the patient arrives to the clinic. The date, time and the time the subject took the study medication must be collected on the eCRF. If logistically not possible the sample may be collected by a visiting nurse or equivalent.

4-a In Period 2, the subject must have a follow up visit as soon as possible within 24 hours of the dose for ECG & to collect PK samples. The sample must be collected as soon as the patient arrives to the clinic. If logistically not possible the sample may be collected by a visiting nurse or equivalent. The date, time and the time the subject took the study medication must be collected on the eCRF. In case the follow-up visit in Period 2 falls on a weekend, a window of up to 48 hours may be considered.

 A second PK sample will be collected 1-2 hours after the 1st sample was collected; the collection time of PK samples must be entered in eCRF. The second PK can be optional if not logistically possible.

 If subject is not domiciled in a clinic for the study, the study drug and instructions for use will be dispensed to the subject to be used as out-patient.

 Subjects will take 2 injections (in Cohort 1) / 1 injection (in cohort 2) of SOM230 or placebo s.c. in each study Period (1 &2) as instructed. These injections must be administered at the same time one after the other. The date and time of dose must be recorded on the patient diary.

 Diary: issued at screening visit; baseline information should be collected only for last 3 days prior to the baseline visit. Diary will be reviewed at the clinic visits.

 Blood chemistry should be repeated if Baseline Visit is greater than 10 days from Screening Visit.

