 The EOS visit will occur 3 days after Period 2, post study drug administration.

 At the Investigator's discretion, optional screening ECG may be performed. The baseline ECG is optional, if screening ECG is done within not more than 7 days, and there is no change in medications. All subjects must have one ECG performed, either at screening or baseline, prior to the treatment phase.

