## **Adverse events**

All information obtained on adverse events will be displayed by treatment and subject.

The number and percentage of subjects with adverse events will be tabulated by body system and preferred term with a breakdown by treatment. An adverse event starting in one period and continuing into the next period is counted only in the onset period. A subject with multiple adverse events within a body system is only counted once towards the total of this body system.

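### The AE table compares placebo and SOM230 over unequal follow-up, so in expectation more background AEs are counted under SOM230; a supplementary table with equal windows would show how much.

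*SAP*

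**What the plan says.** SAP 7.1.2 (Adverse events) plans the number and percentage of subjects with AEs, "tabulated by body system and preferred term with a breakdown by cohort and treatment". Protocol 11.5.2 plans the same table by treatment, and both documents assign events by onset: "An adverse event starting in one period and continuing into the next period is counted only in the onset period".

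The order is fixed. Protocol 3.1 states: "Two consecutive attacks will be treated: first attack will be treated with placebo (Period 1) and the following attack will be treated with SOM230". A subject with no attack in the "72 hours post Period 1 treatment the subject will be excluded from the study", which caps Period 1. Entry requires subjects "averaging 2-6 headache attacks per day each lasting at least 45 minutes without treatment" (Protocol 4.1).

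After SOM230, Table 8-1 footnote 10 says "The EOS visit will occur 3 days after Period 2, post study drug administration". Footnote 2, for subjects who need standard-of-care treatment or have a recurrent attack, says "every effort must be made to discontinue the subject after 24 hours of taking the study medication", with End of Study evaluations done at that point. Protocol 6.9 adds, for subjects who need rescue other than oxygen: "Every effort must be made to obtain study data for at least 24 hours after study medication has been administered".

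The safety set is everyone who received any study drug (SAP section 4). The visible text gives no common risk window, no exposure-adjusted rate and no follow-up length by column for this table.

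**The concern.** Percentages of subjects with an event can be compared directly only when both columns are observed for similar lengths of time. Here a headache, cold or stomach upset unrelated to treatment has a few hours in which to be counted under placebo and one to three days under SOM230. Part of any SOM230 excess would then reflect follow-up time alone.

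Safety and tolerability of SOM230 is a secondary objective, the study informs whether to continue development, and placebo is the table's only reference column. The rationale in Protocol 3.2 accepts that treatment and period are confounded because the periods are close together. It does not address unequal observation time for AEs, which the analysis can handle.

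**Working it through.** The plan states no figure for AE follow-up or background rate, so there is nothing to reproduce.

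**Inputs from the documents**
- Placebo window, subjects dosed in both periods: it ends at the SOM230 dose (inferred from the fixed order and the onset-period rule), at most 72 h. Mean gap = 24 / attacks per day: 24/6 = 4 h to 24/2 = 12 h. This assumes treated attacks come at the entry rate.
- SOM230 window: 72 h as scheduled, about 24 h if stopped early.
- Window ratio, SOM230 to placebo: 72/12 = 6 to 72/4 = 18 as scheduled; 24/12 = 2 to 24/4 = 6 if everyone stops at 24 h.

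**Assumed:** background rate r = 0.02 or 0.10 AEs per subject-day, constant, with no drug effect.

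**1. Subjects dosed in both periods.** Share with at least one background AE = 1 - exp(-r × days).

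| | r = 0.02 | r = 0.10 |
|---|---|---|
| Placebo, 4 h to 12 h | 0.33% to 1.00% | 1.65% to 4.88% |
| SOM230, 24 h | 1.98% | 9.52% |
| SOM230, 3 days | 5.82% | 25.92% |
| Excess at 3 days (points) | 4.8-5.5 | 21.0-24.3 |
| Excess at 24 h (points) | 1.0-1.6 | 4.6-7.9 |

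In 23 subjects (the number in Protocol 11.6), treating the two counts as independent binomials, the SOM230 count is higher in 67-72% of cohorts at r = 0.02 and 97-99% at r = 0.10 with 3-day follow-up. With 24 h follow-up this falls to 31-35% and 62-81%. At r = 0.02 and 24 h a tie is the likeliest result (56-61%).

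**2. Safety set.** The placebo column also holds subjects who never reach SOM230. As an upper case, let the planned 20% drop-out (Protocol 11.6) all be placebo-only with 72 h follow-up. Placebo share = 0.8 × [1 - exp(-r × gap)] + 0.2 × [1 - exp(-3r)].
- r = 0.02: 1.43% (4 h) to 1.96% (12 h). Excess 3.9-4.4 points at 3 days, 0.02-0.55 at 24 h.
- r = 0.10: 6.51% to 9.09%. Excess 16.8-19.4 points at 3 days, 0.4-3.0 at 24 h.

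**3. When it vanishes or reverses.** A 72 h gap with 3-day SOM230 follow-up gives 0. A 48 h gap with 24 h SOM230 follow-up gives -1.9 points (r = 0.02) and -8.6 (r = 0.10).

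**4. Does an equal window repair it?** Simulation: exponential gaps with mean 12 h, kept below 72 h; half the subjects followed 24 h after SOM230 and half 72 h; r = 0.10. With 10% acute events after each dose, the planned table shows about 14% placebo against 26% SOM230; the common window shows 14.0% against 14.0%. With a true acute difference of 10% against 30%, the common window shows 14.0% against 33.1%, so the acute signal is kept. SOM230 follow-up is shorter than the gap in 6.7% of subjects, so the shorter window must be taken per subject.

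**The case against.** **The size is uncertain.** Neither AE rate is in the documents, and the 4-12 h gap is inferred from an average at entry. The table uses the safety set, where placebo-only subjects lengthen the placebo column. Footnote 2 can be read as covering any recurrent attack; at 2-6 attacks per day recurrence within 72 h would be common, so 24 h follow-up might be usual. All of this stands. It is why both follow-up lengths and both populations are shown, and why the 3-day figures should not be read alone. It does not remove the direction: even with 20% placebo-only and everyone stopping at 24 h, the expected excess is near zero or positive at 4-12 h gaps.

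**Little turns on the table.** The study is non-confirmatory, the table has no test, the visible stopping rules use related serious events and judgement, and relatedness and dates are recorded for each event. This stands and limits the priority.

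**Stronger readings to avoid.** A reader might infer that the table overstates AEs caused by SOM230. It does not; the issue is how background events are split between the columns. A reader might also infer that the plan has no AE cut-off. That cannot be concluded: the body of Table 8-1 is missing from the text reviewed and parts of the SAP are redacted, so a cut-off may sit there.

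**Conclusion.** The point holds for direction and less firmly for size. Followed as written, the table compares columns with different observation times and, in expectation, puts more background AEs under SOM230. This rests on the fixed order, the onset-period rule, and treated attacks arriving near the entry rate. The excess ranges from almost nothing (low rate, 24 h SOM230 follow-up, many placebo-only subjects) to over 20 points (0.10 per day, full 3-day follow-up, subjects dosed twice), and it reverses where placebo gaps exceed SOM230 follow-up. The documents do not show which case will apply. For an untested descriptive table in a non-confirmatory study the priority is minor to moderate.

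**What to change.** In SAP 7.1.2:
- Keep the full-follow-up AE table as the main safety display. Footnote the number of subjects and the median and range of follow-up in each column, with placebo-only subjects shown separately.
- Add one supplementary table for subjects dosed in both periods. Count AE onsets after each dose over the same length of time: the shorter of that subject's Period 1 (placebo dose to SOM230 dose) and that subject's actual SOM230 follow-up.
- Record AE onset time for events that start on a dosing date; Protocol 9.1 lists only start and end dates. If the time is missing on a day with both doses, show two bounds: all such events to placebo, then all to SOM230. Counting each under both treatments would pull the columns together.

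**Cost:** one extra table, one footnote and one CRF field. The time field matters: if the placebo dose is equally likely at any hour, both doses share a date for 1 - 12/24 = 50% of subjects at a 12 h gap and 1 - 4/24 = 83% at 4 h. The existing onset-period rule already needs this information.

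**Limits:** the short window misses later-onset SOM230 events. If onset averaged 6 h (assumed, exponential), the share missed is 6/(6 + 12) = 33% at a 12 h mean gap and 6/(6 + 4) = 60% at 4 h, so the table stays supplementary. Fixed-order confounding remains, as does unequal questioning, because the Period 1 follow-up visit is optional.
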